7.2.1.8 Adverse Event Collection Period

All adverse events reported from the time of study drug administration until 49 days following discontinuation of study drug administration have elapsed will be collected, whether solicited or spontaneously reported by the subject.

In addition, serious and non-serious adverse events occurring after the subject signed the study-specific informed consent and prior to the initial dose of study drug will be collected only if they are considered by the Investigator to be causally related to required study procedures.

Adverse event information will be collected as shown below.

Adverse Event Collection

Protocol Related SAEs and Nonserious Adverse Events*	Serious and Nonserious Adverse Events Elicited and/or Spontaneously Reported		
Consent Signed	Study Drug Start	Study Drug Stopped	49 Days After Study Drug Stopped**

* Only if considered by the Investigator to be causally related to study-required procedures.

**If an AE/SAE occurs more than 49 days after study drug was stopped, it only needs to be reported if it is considered to have a reasonable possibility to be related to the protocol treatment or study participation.

7.2.1.9 Serious Adverse Event Reporting

In the event of a serious adverse event, whether associated with study drug or not, the Investigator will notify the AbbVie Oncology Clinical Safety Management Team within 24 hours of the site being made aware of the serious adverse event. Notification to AbbVie will be done by submitting the paper SAE forms to the email or fax specified below.

FAX to: [REDACTED]

Email: [REDACTED]

In order to be compliant with regulatory reporting requirements, all initial SAE reports should always include the following minimal information:

- Name of person sending the report (i.e., name, address of Investigator)
- Patient identification (screening/randomization number, NOT patient name or initials)
- Protocol number
- Description of SAE
- Causality assessment

All applicable forms need to be dated and signed by the principal investigator (PI) or designated sub-investigator (Sub-I).

For serious adverse event concerns, contact the Oncology Safety Team at:

Safety Management Oncology
AbbVie
[name]
[REDACTED]
[name]

Contact Information:

[REDACTED]

EORTC Clinical Research Physician:

[REDACTED]

For any subject safety concerns, please contact the listed below:

In case of subject safety concerns or medical emergencies the individuals noted above are unavailable, please call the following central back-up number:

Phone: [REDACTED]

The Sponsor will be responsible for Suspected Unexpected Serious Adverse Reactions (SUSAR) reporting for the Investigational Medicinal Products (IMP) ABT-414, Lomustine and Temozolomide in accordance with Directive 2001/20/EC. The reference documents used for SUSAR reporting in the EU countries will be the most current version of the Investigator's Brochure for ABT-414 and Summary of Product Characteristics (SmPC) for Lomustine and Temozolomide.

7.2.1.10 Pregnancy

Pregnancy in a study must be reported to AbbVie within 1 working day of the site becoming aware of the pregnancy. This applies to subjects who become pregnant during the study while on study drug or within 49 days post study drug discontinuation.

Subjects who become pregnant during the study must be discontinued (section 5.4).

Information regarding a pregnancy occurrence in a study subject and the outcome of the pregnancy will be collected.

Male subjects should be informed that contraceptive measures should be taken by their female partners. If the subject's partner should become pregnant during the study, this should also be reported and data may be collected. In the event of pregnancy occurring in the partner of an enrolled subject, written informed consent for release of medical information from the partner must be obtained prior to the collection of any pregnancy-specific information and the pregnancy will be followed to outcome.

Pregnancy in a study is not considered an adverse event. However, the medical outcome of an elective or spontaneous abortion, stillbirth or congenital anomaly is considered a serious adverse event and must be reported to AbbVie within 24 hours of the site becoming aware of the event.

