proportional. ABT-414 serum exposure was moderately lower than that of total ABT-806. In M13-379, for dose-normalized C_{max}, cys-mcMMAF was approximately 400 -fold lower than that of ABT-414 in molar concentration. The observed harmonic mean terminal phase elimination half-life ranged approximately from 7.5 to 12 days and 9 to 15 days for ABT-414 and total ABT-806, respectively. The observed mean clearance of ABT-414 ranged approximately from 0.19 to 0.37 mL/h/kg. The observed harmonic mean terminal phase elimination half-life of cys-mcMMAF was approximately 4 days.

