- For non-operated patients, recurrent disease must include at least one bi-dimensionally measurable contrast-enhancing lesion with clearly defined margins by MRI scan, with minimal diameters of 10 mm, visible on 2 or more axial slices 5 mm apart, based on an MRI scan done within 2 weeks prior to randomization
- Stable or decreasing dosage of steroids for 7 days prior to the baseline MRI scan
- No current or recent (within 4 weeks before randomization) treatment with another investigational drug
- Patients who require anti-convulsant therapy must be taking non-enzyme inducing antiepileptic drugs (non-EIAED). Patients previously on EIAED must be fully switched to non-EIAED at least 2 weeks prior to randomization
- No underlying or previous conditions that could interfere with treatment, including but not limited to:
 - no evidence of active infection requiring hospitalization or antibiotics, within 2 weeks prior to randomization
 - no active infectious keratitis
 - no other diseases interfering with follow up
- No planned vaccinations with live vaccines
- Adequate hematological function defined as: neutrophils $\geq 1.5 \times 10^9$ cells/L and platelets $\geq 100 \times 10^9$ cells/L and hemoglobin ≥ 6.2 mmol/L (9.9 g/dl)
- Normal liver function: bilirubin $< 1.5 \times$ upper limit of the normal range (ULN), alkaline phosphatase and transaminases (ASAT) $< 2.5 \times$ ULN
- Renal function: calculated creatinine clearance ≥ 30 mL/min by the Cockcroft-Gault formula (see [Appendix E](#))
- Absence of pregnancy. Women of childbearing potential (WOCBP) must be using an adequate method of contraception to avoid pregnancy throughout the study and for 6 months beyond the end of treatment in such a manner that the risk of pregnancy is minimized. In general, the decision for appropriate methods to prevent pregnancy should be determined by discussions between the investigator and the study subject. WOCBP include any female who has experienced menarche and

who has not undergone successful surgical sterilization (hysterectomy, bilateral tubal ligation, or bilateral oophorectomy) or is not postmenopausal. Females should not be breastfeeding.

- Post menopause is defined as: amenorrhea ≥ 12 consecutive months without another cause or for women with irregular menstrual periods and on hormone replacement therapy (HRT), a documented serum follicle stimulating hormone (FSH) level > 35 mIU/mL

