- Women who are using oral contraceptives, other hormonal contraceptives (vaginal products, skin patches, or implanted or injectable products), or mechanical products such as an intrauterine device or barrier methods (diaphragm, condoms, spermicide) to prevent pregnancy, or are practicing abstinence or where their partner is sterile (e.g., vasectomy) should be considered to be of childbearing potential.
- Women of childbearing potential must have a negative serum or urine pregnancy test (minimum sensitivity 25 IU/L or equivalent units of HCG) within 72 hours prior to randomization.
- Female patients within one year of entering the menopause must agree to use an effective non-hormonal method of contraception during the treatment period and for at least 6 months after the last study treatment.
- Males must agree to use an effective method of contraception during the treatment period and for at least 6 months after the last study treatment.
- Before patient randomization and study related procedures (that would not have been performed as part as standard care), written informed consent must be given according to ICH/GCP, and national/local regulations.
- Patients with a buffer range from the normal values of $\pm 5\%$ for hematology and $\pm 10\%$ for biochemistry are acceptable. A maximum of ± 2 days for timelines are acceptable (with the exception of the pregnancy test).

Important note: All eligibility criteria must be adhered to, in case of deviation discussion with Headquarters and study coordinator is mandatory.

4 Study Procedures

This is a randomized open label multicenter phase II trial (see objectives in chapter 2).

For detailed statistical considerations, see chapter 8.

Patients will be randomized at the EORTC headquarters **after verification of the eligibility criteria (see chapter 3)** to receive one of the following:

Arm 1: patients will be treated with ABT-414 1.0 mg/kg IV infusion over 30 to 40 minutes once every 2 weeks in combination with TMZ 150 mg/m² day 1 to 5, for the first 28-day cycle, with dose escalation to 200 mg/m² in subsequent cycles in case of adequate tolerance and until one of the treatment withdrawal criteria has been met. In this Arm 1 the schedule of clinical and lab assessments follows the cycle of TMZ (a delay of TMZ delays the assessment schedule, withholding ABT-414 does not affect the assessment schedule).

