- Absence of pregnancy. Female subjects of childbearing potential must be using an adequate method of contraception to avoid pregnancy from Study Day 1 throughout the study and for 6 months beyond the end of treatment in such a manner that the risk of pregnancy is minimized. In general, the decision for appropriate methods to prevent pregnancy should be determined by discussions between the investigator and the study subject. Female subject of childbearing potential includes any female who has experienced menarche and who has not undergone successful surgical sterilization (hysterectomy, bilateral tubal ligation, or bilateral oophorectomy) or is not postmenopausal. Female subjects of non-childbearing potential do not need to use birth control.
Pediatric female patients are not considered to be of child bearing potential if meeting any of the following criteria:
 - Permanently surgically sterile (bilateral oophorectomy, bilateral salpingectomy, or hysterectomy).
 - Females who have not experienced menarche (at least one menstrual period).
 - Female subjects of childbearing potential must have a negative serum or urine pregnancy test (minimum sensitivity 25 IU/L or equivalent units of HCG) within 72 hours prior to enrollment.
 - Female subjects must not be **pregnant, breastfeeding, or considering becoming pregnant** during the study or for at least 6 months(5 \times the half-life of AbbVie product or 30 days, whichever is longer, plus an additional 30 days to the 5 half-lives, if genotoxic) after the last dose of study drug.

- Male subjects that are **sexually active with female partner(s) of childbearing potential** must agree to use an effective method of contraception from Study Day 1, during the treatment period and for at least 6 months after the last study treatment.
- Male subjects must not be considering **fathering a child or donating sperm** during the study or for at least 6 months after the last dose of study drug.
- Before patient registration, enrollment and study-related procedures that would not have been performed as part as standard care, written informed consent must be given according to ICH/GCP, and national/local regulations.
- Subject must not have a history of a major immunologic reaction to any IgG-containing agent.

Important note: All eligibility criteria must be adhered to, in case of deviation discussion with the study coordinator is mandatory.

Pre-Enrollment Recommendations to Support Efficacy Evaluation:

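### A female subject's pregnancy is reportable only if it starts within 49 days of stopping study drug, so about 73% of the 6-month post-treatment contraception period carries no routine reporting duty

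*Protocol*

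**What the plan says.** Section 7.2.1.10 gives the site one working day to notify the sponsor of a pregnancy and defines which pregnancies count: "This applies to subjects who become pregnant during the study while on study drug or within 49 days post study drug discontinuation". It then says: "Information regarding a pregnancy occurrence in a study subject and the outcome of the pregnancy will be collected". For partners of male subjects it uses another phrase: "If the subject's partner should become pregnant during the study, this should also be reported and data may be collected". The section also states that pregnancy is not itself an adverse event, but that abortion, stillbirth or congenital anomaly is a serious adverse event to be reported within 24 hours of the site becoming aware.

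The contraception period is longer. Under section 3.2, a woman able to conceive "must be using an adequate method of contraception to avoid pregnancy throughout the study and for 6 months beyond the end of treatment". For men: "Males must agree to use an effective method of contraception during the treatment period and for at least 6 months after the last study treatment". The protocol summary repeats these criteria. Appendix I sets the same 6 months for pediatric subjects.

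Section 7.2.1.8 collects all adverse events up to 49 days after study drug. Later events need reporting only if they are thought possibly related to treatment or study participation. Section 6.4 schedules follow-up every 12 weeks until death or loss to follow-up. Its list of items does not include pregnancy.

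**The concern.** The protocol treats the 6 months after treatment as a time when pregnancy should be avoided, but the duty to notify one in a female subject ends at day 49. Neither document explains the difference. The 49 days equals the general adverse event window in section 7.2.1.8, so it may simply have been carried over from there.

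At stake is information on fetal exposure. A site that follows section 7.2.1.10 exactly need not report a conception on day 60. If the pregnancy is not notified, its outcome may never be known. Normal outcomes, which any estimate of risk needs as its denominator, would be missing as well. Such data may be impossible to recover later.

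**Working it through.** The plan states no figure for this gap, so there is none to reproduce.

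**Share of the post-treatment period without a routine duty**

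Inputs: 49 days (7.2.1.10); 6 months (3.2); 1 month = 30.4375 days (SAP section 6.0).

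- 6 × 30.4375 = 182.6 days
- Uncovered: 182.6 − 49 = 133.6 days
- Share: 133.6 / 182.6 = 73.2%
- With 6 months taken as 180 days: 131 / 180 = 72.8%. As 184 days: 135 / 184 = 73.4%.

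**Share of the whole contraception period**

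Contraception is also required on treatment, when pregnancies are reportable. With t months on treatment the uncovered share is 133.6 / (30.4375 × t + 182.6):

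| Assumed t (months) | Uncovered share |
|---|---|
| 2.6 (assumed control median PFS, section 8.3) | 51% |
| 4.8 (assumed ABT-414 median PFS, section 8.3) | 41% |
| 12 (illustrative) | 24% |

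**A conception on day 60 in a female subject, taken through the text**

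1. Section 3.2: day 60 is within the 6 months, so contraception was required.
2. Section 7.2.1.10: day 60 is after day 49, so there is no notification duty.
3. Section 7.2.1.8 cannot capture the pregnancy, because 7.2.1.10 says it is not an adverse event.
4. A later loss, stillbirth or anomaly is a serious adverse event, but after day 49 section 7.2.1.8 asks for it only if judged possibly related.
5. Section 6.4 does not prompt the site to ask.
6. Appendix I applies adult rules unless it addresses a point. It is silent on pregnancy reporting, so the 49 days carries over to pediatric subjects.

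**Partners of male subjects**

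The partner sentence has no 49-day limit. Section 5.4 keeps patients on study after treatment stops, and section 6.4 follows them until death or loss to follow-up, which suggests a long window. Section 8.5, however, allows the study to end once 49 days have passed since all patients stopped treatment, provided its other two conditions are met. For the last patients treated, that could be a short window. The text does not say which meaning applies.

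**Do the existing contacts cover the period?**

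Contacts fall at 12 × 7 = 84, 168 and 252 days, each ± 14 days. The second is at day 182 at the latest, just before day 182.6. A conception late in the window, or not yet recognised at the second contact, is first asked about at the third, at about day 252.

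**The case against.** The strongest case on the other side is that a precautionary contraception period and a notification window serve different purposes, so a difference between them is not in itself a contradiction. The 49 days matches the adverse event period and the second end-of-treatment visit. Events will be very few: assumed median control survival is 7 months, and some later pregnancies would be confounded by further therapy. All of this stands. It limits the importance of the point, but it does not explain why exposure inside the protocol's own contraception period should go unreported.

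Several stronger readings are tempting, and the documents do not support them:

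- *Late pregnancies are never collected.* Possibly related losses and anomalies stay reportable after day 49. The general collection sentence ("Information regarding a pregnancy occurrence in a study subject and the outcome of the pregnancy will be collected") also carries no time limit of its own. It follows the scope sentence and is most naturally read within it. If it is meant to be unlimited, the section conflicts with itself and still needs clarifying.
- *Outcome follow-up stops at day 49.* The 49 days limits when the pregnancy must begin. The outcome of one that began by then is still collected.
- *The 49-day limit also covers partners.* It is written for subjects who become pregnant.
- *Forty-nine days is too short by the protocol's own pharmacokinetics.* Section 1.6 says of ABT-414: "The observed harmonic mean terminal phase elimination half-life ranged approximately from 7.5 to 12 days". Five half-lives are then 5 × 7.5 = 37.5 to 5 × 12 = 60 days. For total ABT-806 they are 5 × 9 = 45 to 5 × 15 = 75 days. Forty-nine days lies inside both ranges, and it is about 12 half-lives of cys-mcMMAF (49 / 4). The shortfall appears only towards the upper ends, so this is not a main support.

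**Conclusion.** The point holds as a gap in safety reporting for female subjects, adult and pediatric. A conception from about day 50 to day 183, which is 73% of the post-treatment contraception period (72.8% to 73.4% depending on month length), has no routine reporting or follow-up duty. The 73% should not be quoted for the whole contraception period. With 2.6, 4.8 or 12 months on treatment the share is about 51%, 41% or 24%, and those durations are assumptions. For partners of male subjects the finding is only that the time phrase is undefined.

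The number of affected pregnancies will be very small. The point has no bearing on sample size, power or any efficacy analysis. It is worth making because the rule, followed exactly, produces the gap and the repair is cheap. It takes no view on what the contraception period itself should be.

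**What to change.** 1. Reconcile section 7.2.1.10 with sections 3.2 and 7.2.1.8 and Appendix I, so that the reporting window for a subject's pregnancy is at least as long as the protocol's own post-treatment contraception period, with follow-up to outcome. State that it applies to pediatric subjects by reference.
2. Define the time phrase in the partner sentence so that it covers at least the same period and does not narrow the present text.
3. Add a pregnancy question to the section 6.4 contacts, up to and including the first one after the window closes (about day 252). Appendix I has its own 6-monthly long-term follow-up, so the question should be added there on the same principle.
4. Say how that last contact is made if the study could close under section 8.5 before it falls due.

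Cost: a few sentences, one question at contacts that already exist, and a very small number of extra pregnancy reports. No change to the SAP's efficacy analyses is needed.

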7.2.1.11 Toxicity Management

For the purpose of medical management, all adverse events and laboratory abnormalities that occur during the study must be evaluated by the Investigator. The table of clinical toxicity grades modified from the National Cancer Institute Common Terminology Criteria for Adverse Events (NCI CTCAE) Version 4.0 is to be used in the grading of adverse events and laboratory abnormalities that are reported as adverse events, each of which will be followed to satisfactory clinical resolution.

7.3 Evaluation of Quality of Life

Quality of life assessment is described in detail in chapter 10.

8 Statistical considerations

8.1 Statistical design

8.1.1 Sample size

This is a comparative randomized open label multicenter/multiarm phase II trial. Overall Survival (OS) is the primary endpoint.

Based on literature review, a median OS of 7 months is expected in the mixed control arm (lomustine or TMZ). Based on a one-sided logrank test, at an overall significance level of 2.5% and a power of 91.7% (accounting for the global testing strategy), a total of 170 deaths (118 per comparison, i.e. monotherapy ABT-414 versus control and combination ABT-414 + TMZ versus control) are needed to detect an increase of median OS to 12.9 months in the treatment arms corresponding to a Hazard Ratio (HR) equal to 0.54 (i.e. a reduction in the hazard of death of 46%). Assuming a monthly accrual of 10 patients during month 1 to 12 and 20 patients per month after 12 months, 240 patients can be recruited within 18 months. A follow-up duration of 13 months after end of accrual is required to observe the 170 deaths.

There will be an interim futility analysis organized after observation of 45 PFS events (see section 8.3).

Provided that PFS and OS effects are independent, the overall power of the study is estimated to be approximately 85%. However, treatment effect on PFS and on OS may reasonably be assumed to be positively correlated, and hence the overall power of the study accounting for the interim analysis is expected to exceed 85%.

8.1.2 Randomization and stratifications

All patients entered in this trial will be centrally randomized at the EORTC Headquarters (for practical details, see section 13.3 on randomization procedure). The minimization technique (Ref. 37) used by the EORTC for random treatment allocation is based on the variance method with semi-random assignment dependent on a preset threshold as implemented by Freedman and White (Ref. 38). However, per suggestion of the ICH E9 statistical guidelines, the algorithm has been modified to incorporate a random allocation component in order to ensure an additional 15% of completely random assignments.

In this trial, the threshold is set to 3, the total number of stratification factors.

Stratification factors are:

- Regions of the world (North America (USA, Puerto Rico & Canada) vs Europe and Australia vs Asia/other regions)
- WHO Performance Status (0 vs >0)
- Timing of relapse (< 16 weeks vs \geq 16 weeks after the first day of the last TMZ cycle)

8.2 Statistical analysis plan

8.2.1 Primary and secondary endpoints

8.2.1.1 Primary endpoint

The primary endpoint is OS at the final analysis and Progression Free Survival (PFS) according to RANO criteria and assessed by IRC at the interim analysis. In addition to the OS Hazard Ratio, the following parameters will be assessed: median OS, probability of survival at 1 year (OS12), probability of survival at 2 years (OS24). See chapter 1 for the definition of endpoints.

